symptom score³ and nasal/throat/chest score on days 1, 3, 5 and 7 of observation – according to physician’s objective examination; on days 1-7 of observation – according to patient’s diary).

6. Number of intakes of antipyretic drugs according to indications on days 1, 2, 3, 4 and 5 of therapy.
7. Changes in viral load⁴ during the treatment and follow-up periods.
8. Percentage of patients with exacerbation of the disease course (complications requiring antibiotic drugs or hospitalization).

Safety assessment

- Presence and nature of adverse events during therapy, their relationship with the product and other characteristics.

Study design

Study design: multicenter double-blind placebo-controlled randomized parallel-group study.

The study will enroll outpatients of both genders aged 3-12 years with clinical signs of influenza/ARVI including fever $\geq 38.0^{\circ}\text{C}$ seeking for medical advice within the first day after the disease debut. The first visit shall be made at the subject’s home. After signing patient information sheet (informed consent form) by the parent/adoptive parent for the subject’s participation in the study his/her medical history will be collected, objective examination will be performed and concomitant therapy will be recorded. Nasal swab for rapid influenza diagnostics will be collected. In case of positive rapid test the physician will take nasal and oropharyngeal swabs (nasopharyngeal swab) for further PCR diagnosis of influenza A and/or B to determine the viral load. In case of negative result of rapid test the physician will take nasopharyngeal swab for further PCR to detect other respiratory viruses.

If the subject meets inclusion criteria and has no exclusion criteria at visit 1 (Day 1) he/she shall be enrolled and randomized into one of the two groups: group 1 will receive Anaferon for children for 5 days; group 2 – placebo according to Anaferon for children for 5 days. Parent/adoptive parent will receive a diary to record axillary temperature of the subject on a daily basis in the morning and evening (temperature is measured with a standard non-mercuric

³ **Total symptom score** is calculated based on intensity of each influenza symptom at subsequent statistical treatment by the experts of OOO “NPF “Materia Medica Holding”.

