⁴ Viral load will be evaluated in subjects with positive rapid test for influenza A and B. Viral RNA levels [influenza A/B] \log_{10} copies/mL in nasal and oral swabs will be determined by real-time RT-PCR.

thermometer Geratherm Classic) as well as intensity of the disease symptoms. Training on the diary filling will be performed for parents/adoptive parents.

The subject will be followed for 14 days (screening, randomization – 1 day, treatment – 5 days, follow-up – 1 day; delayed phone “visit” – day 14).

During the treatment and follow-up periods the subject/physician shall make 4 visits, the fifth phone “visit” is stipulated additionally: 1) physician/subject visits – on days 1, 3, 5 and 7 (Visits 1, 2, 3 and 4) – at medical facility or at home; 2) phone “visit” (Visit 5) – on day 14.

At visits 2-4 the physician shall record objective examination findings, collect nasopharyngeal swabs for further PCR diagnosis in subjects with positive rapid test (to determine viral load and its reduction against therapy), monitor the prescribed and concomitant therapy, revise the patient’s diary. Phone “visit” will be made to inquire on the subject’s condition, presence/absence of secondary bacterial/viral complications, administration of antibacterial drugs.

Symptomatic therapy and therapy of co-morbidities is allowed except for the products specified in section “Prohibited concomitant therapy”.

Inclusion and exclusion criteria

Inclusion criteria

1. Subjects of both sexes aged 3-12 years inclusively.
2. Diagnosis of influenza/ARVI according to physician’s examination: body temperature $\geq 38.0^{\circ}\text{C}$ at the time of examination + symptom score ≥ 4 (at least 1 systemic symptom ≥ 2 and 1 nasal/throat/chest symptom ≥ 2 or several symptoms ≥ 1 score).
3. The first 24 hours from the beginning of manifestations of influenza/ARVI.
4. The possibility to start therapy within 24 hours from the first symptoms of ARVI.
5. Availability of patient information sheet (informed consent form) for parents/adoptive parents for participation in the study signed by one of the parents/adoptive parents.

Exclusion criteria

1. Suspected pneumonia, bacterial infection or severe disease requiring antibacterial products (including sulfanilamides) starting from the first day of the disease.
2. Clinical symptoms of severe influenza/ARVI⁵ requiring hospitalization.

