Study design scheme

Schedule of study procedures

Procedure/Visit	Visit 1 (Day 1)	Visit 2 (Day 3)	Visit 3 (Day 5)	Visit 4 (Day 7)	Visit 5 (Day 14±1)
Obtaining signed informed consent form (ICF)	+				
Collection of complaints	+	+	+	+	
Collection of medical history	+				
Objective examination	+	+	+	+	
Recording influenza/ARVI symptoms	+	+	+	+	
Inclusion/exclusion criteria assessment	+				
Recording concomitant therapy	+	+	+	+	
Rapid test for influenza viruses in nasal swabs	+				
Obtaining nasal and oropharyngeal	+	+	+	+	

swabs for PCR diagnosis of influenza (in case of positive result of rapid test for influenza)					
Obtaining nasal and oropharyngeal swabs for PCR diagnosis of other respiratory viruses (in case of negative result of rapid test for influenza)	+				
Randomization and prescription of the study therapy	+				
Issue of the study product	+				
Issue of antipyretic product	+				
Accounting and return of the study product, determination of compliance				+	
Issue of patient's diary	+				
Revision of correctness of diary filling		+	+	+	
Diary return				+	
Therapy safety assessment		+	+	+	+
Phone contact					+

Statistical Analyses

Samples

Statistical analysis will be carried out in the following sets:

Total set – all enrolled subjects whose parents/adoptive parents had signed ICF. This set will take into account all adverse events and related conditions during the study including prior to the study therapy initiation.

Total set of the subjects receiving at least one dose of the study product will be used for safety and tolerability analysis (Safety population), as all adverse events recorded in the subject after administration of the product will be taken into account.

Full Analysis Set. This set includes all enrolled subjects excluding those having at least one of the following events:

- 1) non-compliance with inclusion/exclusion criteria;
- 2) the subject did not receive a single dose of the study product;
- 3) lack of any data on the subject after prescription of the study product

This set most fully conforming to Intention-to-treat principle will be used for Intention-to-treat analysis (ITT-analysis) of the study product efficacy.

Per Protocol set. This set includes all subjects receiving per protocol therapy in full, completing all scheduled visits and having no major deviations from the protocol. This set will be used for Per Protocol analysis (PP-analysis) of the study therapy efficacy.

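### The viral-load population is set by the rapid test alone, although a Day 1 RT-PCR exists in the same children and no rule covers undetectable RNA

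*Combined protocol and SAP*

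**What the plan says.** Secondary endpoint 7 reads "Changes in viral load⁴ during the treatment and follow-up periods". Its footnote 4 names the group, "Viral load will be evaluated in subjects with positive rapid test for influenza A and B", and the scale, log10 copies/mL by real-time RT-PCR.

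Sampling follows the same condition. On Day 1, under Study design, "In case of positive rapid test the physician will take nasal and oropharyngeal swabs (nasopharyngeal swab) for further PCR diagnosis of influenza A and/or B", and the stated aim includes determining the viral load. This step is described before enrolment and randomisation. At Visits 2-4 the physician is to "collect nasopharyngeal swabs for further PCR diagnosis in subjects with positive rapid test (to determine viral load and its reduction against therapy"). The schedule of procedures makes the influenza PCR swabs at Visits 1-4 conditional on the rapid test and on nothing else.

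Under Statistical Analyses, Samples, there are four sets: Total, Safety, Full Analysis and Per Protocol. The Full Analysis Set is introduced with "This set includes all enrolled subjects excluding those having at least one of the following events". Its three exclusions are ineligibility, no dose taken, and no data after prescription. No set refers to PCR status. The only missing-data rule is last observation carried forward, and nothing is said about RNA below the detection limit.

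**The concern.** A reduction endpoint needs something to reduce. The Day 1 RT-PCR is the baseline value of the endpoint itself, yet membership is decided by a different test. If some rapid-positives have no detectable influenza RNA on Day 1, their change from baseline is undefined on a log scale until someone chooses a number.

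- If a floor value is imputed, the change is near zero in both arms. The between-arm difference shrinks by the share of such children. Mixing them with children whose load falls also adds a variance component.
- If they are left out, the analysed group becomes the PCR-positive one, but by a decision that is not written down and could be taken after unblinding.

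Either way, the virological result would rest on a choice that the plan could settle now, with a measurement it already collects.

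**Working it through.** **The plan's own figures.** These concern illness duration, not viral load. With a difference of 0.5 days, SD 2, two-sided 5% and 80% power: n = 2 × (2 × (1.960 + 0.842)/0.5)² = 251.2 per arm. A two-look O'Brien-Fleming inflation of 1.0078 gives 253.1, so 254 per arm and 508 in total. Then 508/(1 − 0.4774) = 972.06. Both stated figures reproduce. The documents give no effect, SD or power for viral load.

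**Inputs for the dilution.**
- Rapid-positive share q, from Evaluation of sample size: one positive to 5-6 negatives, so q = 1/6 (16.7%) or 1/7 (14.3%).
- Sensitivity se (50-80%) and specificity sp (95-100%) of the rapid test: **assumed**, because the documents give neither.
- False-positive children are taken to have no detectable Day 1 RNA and, if analysed, an imputed change of zero.

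**Formulas.** Prevalence π = (q − (1 − sp))/(se + sp − 1). False-positive share of rapid-positives f = (1 − sp)(1 − π)/q. The mean between-arm difference is multiplied by (1 − f).

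Example with q = 1/6, sp = 0.98, se = 0.80: π = (0.1667 − 0.02)/0.78 = 0.188, and f = 0.02 × 0.812/0.1667 = 9.7%.

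| Assumed specificity | f, 1:5, se 50% / 80% | f, 1:6, se 50% / 80% | Children per arm* |
|---|---|---|---|
| 100% | 0 / 0 | 0 / 0 | 0 |
| 99.5% | 2.0% / 2.4% | 2.5% / 2.9% | about 1 |
| 99% | 4.1% / 4.8% | 5.1% / 5.8% | about 2 |
| 98% | 8.3% / 9.7% | 10.4% / 11.8% | about 4 |
| 95% | 22.2% / 25.3% | 27.8% / 30.7% | 9 to 11 |

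*Each share is multiplied by the rapid-positives per arm for the same ratio: 254/6 = 42.3 or 254/7 = 36.3. This assumes that rapid-negative children stay in the trial.

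**Power illustration.** Suppose the endpoint would have 80% power with no false positives, so the expected test statistic is 1.960 + 0.842 = 2.802. Let f = 10%, and let the mean fall in true positives be μ SDs. With zero variance in the false positives, the mixture SD is √[(1 − f)(1 + fμ²)].
- All rapid-positives, μ = 1: SD 0.995; 2.802 × 0.9/0.995 = 2.53; power about 72%.
- All rapid-positives, μ = 2: SD 1.122; 2.802 × 0.9/1.122 = 2.25; power about 61%.
- Day 1 PCR-positives only: 2.802 × √0.9 = 2.66; power about 76% for any μ.

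The smaller group therefore does better once there is an appreciable fall. At μ = 0 the two are equal. The overall SD rises only when the mean fall exceeds about one SD; below that, the loss comes from the shrunken difference.

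**The case against.** The strongest reply is that footnote 4 says who is evaluated, matches the swab rule, and may be no more than a sampling rule. A reader might infer that the plan counts a PCR-negative child as having zero change. It does not say so: log10 copies/mL has no value there without a rule, and the child could equally drop out. This stands, and it is why the point is put as an either/or.

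The size rests wholly on assumed accuracy. It is nil at 100% specificity and small at 99.5%. This stands too.

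The counts per arm are conditional. Evaluation of sample size counts withdrawal at screening for a negative rapid test, whereas Study design provides those children with a PCR for other viruses. If negatives leave, all 508 completers would be rapid-positive, yet 972 enrolled at the stated ratio yields only 139-162 positives (972/7 to 972/6). The documents do not settle this; the percentages do not depend on it. A reader might also multiply the largest share, 31%, by the larger group, 42, and get 13 per arm. Those come from different ratios; matched pairing gives at most about 11.

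A reader might infer that a chance imbalance of false positives would produce a spurious treatment effect. Rapid-test status is fixed before randomisation, so such imbalance is already covered by the test's error rate.

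Finally, a negative Day 1 PCR need not mean a false-positive rapid test. The rapid test uses a nasal swab and the PCR separate nasal and oropharyngeal swabs, within a day of onset. A missed sample could be followed by detectable RNA later. This is a real, small cost of restricting the group. ANCOVA on baseline load could absorb some of the added spread, but the plan does not assign it to this endpoint.

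**Conclusion.** The concern holds as a cheap improvement to one secondary endpoint. The viral-load group is chosen by rapid test alone, the Day 1 RT-PCR is not used to define it, and undetectable RNA has no rule.

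If children without detectable Day 1 RNA are kept with a change near zero, the between-arm difference is attenuated by their share: 2-3% at 99.5% specificity, 4-6% at 99%, 8-12% at 98% and 22-31% at 95%. This assumes 50-80% sensitivity and the plan's 1:5-6 ratio. At 99% down to 95% specificity that is about 2 to 11 children per arm, if rapid-negatives remain in the trial. The direction is certain only if some rapid positives are false, which the documents cannot show.

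The documents do not support reading this as inflated type I error or as a threat to the illness-duration result. The harm is lost precision, attenuation towards no difference, and a choice of population left open.

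**What to change.** Replace the population sentence in footnote 4 with:

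> Changes in viral load will be analysed in randomised children with detectable influenza A or B RNA by RT-PCR in the Day 1 pre-treatment swab. Undetectable values at later visits will be set to a prespecified value based on the assay's detection limit. Results in all rapid-test-positive children will be shown as a sensitivity analysis.

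The detection-limit rule also stops a later undetectable result from being treated as missing and overwritten by last observation carried forward. The sensitivity analysis needs its own stated value for an undetectable Day 1 result.

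Selection on a pre-treatment sample keeps the randomised comparison intact. No new swab, assay or visit is needed. The costs are a slightly smaller number analysed, and that children whose Day 1 swab missed the virus but who later show RNA appear only in the sensitivity analysis.

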14. Subjects whose parents/adoptive parents, according to the investigator's point of view, will not follow the observation requirements during the study or study product dosing regimen.
15. Participation in other clinical studies within 3 months prior to the inclusion in the study.
16. Parent/adoptive parent of the subject is related to the investigator team of medical facility directly involved in the study or is a close relative of the investigator. Close relatives include spouse, parents, children or brothers (sisters) regardless of whether they are biological or adoptive ones.
17. Parent/adoptive parent of the subject is working in OOO “NPF “Materia Medica Holding”, i.e. is the company official, temporary contract worker or an appointed official responsible for the study or their close relatives.

⁶ 1 alcohol unit – 0.33 L light beer/150 mL of unfortified wine, 40 mL of liquors.

Discontinuation criteria

1. Inability or refusal of the subject, his/her parents/adoptive parents to compliance the protocol.
2. Necessity in the medical products not allowed within the study.
3. Development of adverse event requiring the product discontinuation.
4. Subject's or parents'/adoptive parents' wish to terminate the study early due to lack of therapeutic efficacy or any other reason.
5. Cases not specified by the protocol when, according to the investigator, further subject's participation is dangerous.
6. Enrollment of ineligible subject.

Number of subjects

Signed informed consent form is supposed to be obtained from 972 subjects (of them 772 – in the Russian Federation, 100 – in Republic of Belarus and 100 – in Ukraine); this would allow to complete all protocol procedures by at least 508 subjects (n=254 in Anaferon for children and Placebo groups).

Interim analysis

An interim statistical analysis is scheduled within the study. The interim analysis will be based on the findings from examinations and therapy of the protocol-set number of subjects who completed the study. Based on the proposed effect, the minimum required Per Protocol (PP) sample size will be 254 subjects (n=127 in Anaferon for children and Placebo groups).

Treatment

Group 1

Name: Anaferon for children

Active ingredient: affinity purified antibodies to human interferon-gamma – 0.003 g*

** applied to lactose monohydrate as water-alcohol mixture containing no more than 10^{-16} ng/g of the active form of the active ingredient*

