Excipients: Lactose monohydrate 0.267 g, microcrystalline cellulose 0.03 g, magnesium stearate 0.003 g

Dosage: Per os. One tablet per intake (hold in mouth until complete dissolution – regardless of meal). The first 2 hours – every 30 minutes, then 3 additional doses with equal intervals. On days 2-5 – on tablet 3 times a day.

Dosage form: Orodispersible tablets

Description: Flat cylinder-shaped scored beveled edge white to off-white tablets

Storage conditions: Store at temperature below 25°C. Keep out of the reach of children.

Group 2

Name: Placebo

Active ingredient: NA

Excipients: Lactose monohydrate 0.267 g, microcrystalline cellulose 0.03 g, magnesium stearate 0.003 g

Dosage: Placebo using Anaferon for children scheme

Dosage form: Orodispersible tablets

Description: Flat cylinder-shaped scored beveled edge white to off-white tablets

Storage conditions: Store at temperature below 25°C. Keep out of the reach of children

Treatment period

Anaferon for children/Placebo treatment period is 5 days.

Observation period

Overall the subject is observed for 14 days (screening, randomization, treatment initiation – day 1, study therapy period – 5 days, follow-up – 1 day, phone visit – day 14).

Basic therapy

Throughout the study the subject may have symptomatic therapy of influenza/ARVI based on the accepted treatment standards including expectorants, mucolytics, vasoconstrictive nasal drops, where necessary – detoxifying therapy, as indicated* – approved antipyretics**, in case of bacterial complications of influenza/ARVI – antibacterial drugs except for antiviral, immunomodulating and other products specified in section “Prohibited concomitant therapy”.

* Indications for antipyretics products [11, 14, 34]:

Body temperature > 38.5°C;

Body temperature 38.0°C against concomitant chronic pulmonary, cardiac, nervous system diseases.

In case the antipyretic product was prescribed and given to the child by parents/adoptive parents on their own (without physician’s prescription) with no indications, the subject will not be withdrawn. Parents/adoptive parents should record temperature values in patient’s diary prior to the product administration, its name and dose.

** The products allowed as antipyretics (ATC group is specified in brackets):

1. Paracetamol (N02BE01).

2. Ibuprofen (M01AE01).

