Last Observation Carried Forward (LOCF) will be used for filling missing values.

Evaluation of sample size

Evaluation of sample size was based on the following rules and assumptions:

1. Statistical provisions.
 - 1.1 Power of statistical criteria " $P = (1 - \beta)$ " is considered to be equal to 80% (probability of correct rejection of null hypothesis is 0.8).
 - 1.2 Probability of error of the first kind " α " is admitted to be $< 5\%$ (probability of erroneous acceptance of alternative hypothesis is < 0.05).
 - 1.3 The statistical criteria used are two-sided.
 - 1.4 Calculation of total sample size was based on the assumptions on expected effects on primary endpoint claimed in the protocol.
 - 1.5 Effect of interim statistical analyses on probability of error of the first kind is regulated at each point (interim analysis, final analysis) using O'Brien-Fleming boundary.

2. Assumptions on expected clinical study effects.

It is assumed that the difference between average disease duration (until recovery or significant improvement) in Anaferon for children and Placebo groups will be less than 0.5 days, while standard deviation in both groups will not exceed 2 days.

Taking into account that statistical analysis will be performed twice – at interim analysis and at final analysis – based on the assumed effect the minimum required size of each group (product and placebo) will be as follows:

Number of subjects	Interim analysis	Final analysis
Number of subjects in both groups	254	508
including		
- number of subjects in Anaferon group	127	254
- number of subjects in Placebo group	127	254

Given withdrawal at screening, including due to negative rapid influenza test (the ratio is 1 subject with positive test/5-6 subjects with influenza-like symptoms and negative influenza test) and during the study, the final sample size will be 972 subjects to be enrolled.

This calculation is made using the formula: $N_T = N_{PP} / (1 - C_w)$, where N_T – final sample size; N_{PP} – scheduled number of subjects completing the study per protocol ($N_{PP}=508$); C_w – withdrawal coefficient ($C_w=0.4774$).

Interim analysis

Interim analysis of *Particular Per Protocol (pPP)* is scheduled within the study.

Purposes of interim analysis:

- Ability to adjust sample size in case in minor deviation of the effect achieved from the effect specified at baseline;

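### The plan does not secure the complication checks for children who discontinue, and its PP and LOCF rules may then bias endpoint 8 low

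*Combined protocol and SAP*

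**What the plan says.** **Leaving.** Three of the six items under Discontinuation criteria matter most here: item 2, "Necessity in the medical products not allowed within the study"; item 3, "Development of adverse event requiring the product discontinuation"; and item 4, the family's "wish to terminate the study early due to lack of therapeutic efficacy or any other reason". Item 3 speaks of the product only, item 4 of the study itself, and item 2 of neither. Item 5 is about the child's further participation.

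**Follow-up.** Study design states: "The subject will be followed for 14 days". Visits fall on days 1, 3, 5 and 7, with a phone contact on day 14 that asks about the child's condition, complications and antibacterial drugs. Hospitalisation is not named there. The Schedule of study procedures has no early-termination visit and does not say whether later contacts are kept after discontinuation.

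**Endpoint.** Secondary endpoint 8 is "Percentage of patients with exacerbation of the disease course (complications requiring antibiotic drugs or hospitalization"). It has no time window and no rule for children who do not complete.

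**Analysis.** Under Samples, the PP set is defined thus: "This set includes all subjects receiving per protocol therapy in full, completing all scheduled visits and having no major deviations from the protocol". The Full Analysis Set (FAS) keeps an eligible, dosed child who has any data after prescription. The missing-data rule is one sentence: "Last Observation Carried Forward (LOCF) will be used for filling missing values". It names no analysis set and no endpoint, and makes no exceptions.

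**The concern.** Endpoint 8 is a cumulative event: a child either has a complication during follow-up or does not. Carrying the last status forward is a poor rule for such an outcome, because before the event that status is always no event. The rule therefore works in one direction only. It can lose events but cannot add them.

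The children most exposed are those who leave because the treatment seems not to work, because of an adverse event, or because they need a prohibited drug. Those reasons are plausibly linked to later complications and may differ in frequency between arms. If these children are not contacted again, neither analysis set recovers the information: PP leaves them out and LOCF in the FAS counts them as complication-free. The reported complication percentage could then be too low, and the comparison between arms could move in either direction.

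**Working it through.** **1. What the documents allow to be calculated.** No complication rate and no figure for endpoint 8 is given. The nearest figure is the withdrawal coefficient of 0.4774 in Evaluation of sample size. It reproduces the enrolment target: 508 / (1 − 0.4774) = 972.06, stated as 972. The 972 − 508 = 464 children it allows for combine screening losses with on-study losses and are not split. An on-study leaver rate cannot be derived, so everything below rests on assumed values.

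**2. Formulas.** Let p be the complication risk in children who stay, w the share who leave event-free and are not contacted again, and m the ratio of the leavers' later risk to p.

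- True rate: (1 − w)p + w·m·p
- PP rate: p
- FAS rate with LOCF: (1 − w)p
- Share of all events missed under LOCF: w·m / (1 − w + w·m)
- Relative understatement in PP: w(m − 1) / (1 + w(m − 1))

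The last two do not depend on p.

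**3. Results over the assumed range.**

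| w | m | Events missed, LOCF | Understatement, PP |
|---|---|---|---|
| 2% | 2 | 0.04/1.02 = 3.9% | 0.02/1.02 = 2.0% |
| 2% | 4 | 0.08/1.06 = 7.5% | 0.06/1.06 = 5.7% |
| 5% | 2 | 0.10/1.05 = 9.5% | 0.05/1.05 = 4.8% |
| 5% | 4 | 0.20/1.15 = 17.4% | 0.15/1.15 = 13.0% |
| 10% | 2 | 0.20/1.10 = 18.2% | 0.10/1.10 = 9.1% |
| 10% | 4 | 0.40/1.30 = 30.8% | 0.30/1.30 = 23.1% |

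In children, with p assumed between 3% and 10%, the missed events per 254 run from 254 × 0.02 × 0.06 = 0.3 to 254 × 0.10 × 0.40 = 10.2.

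**4. Effect on the arm comparison.** Assume p = 5%, a later risk of 20% in leavers, and 3% leaving on active against 7% on placebo.

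- True: active 0.97 × 5% + 0.03 × 20% = 5.45%; placebo 0.93 × 5% + 0.07 × 20% = 6.05%. Placebo minus active is +0.6 points.
- PP: 5% in both arms, difference 0.
- LOCF: 4.85% and 4.65%, difference −0.2 points.

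The shift under LOCF is 0.8 points. With 254 per arm and a 5% rate, the standard error of the difference is √(2 × 0.05 × 0.95 / 254) = 1.9 points.

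**The case against.** The strongest reply is that the documents are silent, not prohibitive. A reader might infer that discontinued children get no further complication check, or that their later adverse events are not collected. The text says neither. The 14-day follow-up is not limited to children still on product, item 3 stops only the product, safety assessment is scheduled at the Day 14 call, and the Safety population counts events recorded after dosing. The document also calls itself a protocol summary, so a missing procedure is weak evidence that none exists.

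The route out is also narrower than it first seems. Worsening is not itself a discontinuation criterion. Basic therapy allows, "in case of bacterial complications of influenza/ARVI – antibacterial drugs except for antiviral, immunomodulating and other products", so the antibiotic part of endpoint 8 does not force a child out, and hospitalisation is not a discontinuation criterion either. A complication recorded before leaving would carry forward as an event. The LOCF sentence does not say that it is applied to endpoint 8.

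All of this stands, and it limits both the certainty and the size of the point. It does not close the gap. Item 4 is worded as ending the study early. Basic therapy makes an express exception from withdrawal for antipyretics given without indication, which implies that withdrawal of the child, not just of the product, is contemplated elsewhere. Nothing guarantees later contact, and no rule other than LOCF covers the case where contact is lost.

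**Conclusion.** The gap is real and worth closing, although it concerns a secondary endpoint. The plan neither secures the outcome of discontinued children nor says how endpoint 8 is scored when it is missing. By definition PP drops those who do not complete. LOCF, read as written, would count an event-free leaver without further contact as having no complication.

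The amount is unknown. The 4% to 31% of events missed under LOCF holds only for the assumed 2% to 10% leaving and 2 to 4 times the risk. It also assumes that none of these children is contacted again. PP is biased low only if leavers carry the higher risk.

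Two stronger readings are not supported. First, the example above changes the sign of the arm difference, and a reader might take that as a prediction. It is not one: the inputs are assumed, the shift of 0.8 points is less than half of a 1.9-point standard error, and the same inputs give no reversal in PP. Second, a reader might take endpoint 8 as a test of whether withholding antivirals harms children. Prohibited concomitant therapy bars them in both arms, so the arm comparison cannot answer that question.

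**What to change.** 1. In Discontinuation criteria, separate stopping the product from leaving follow-up. This is a rule about data collection and leaves the treatment rules as they are.
2. State that the scheduled Day 14 call is made for every child who took at least one dose, unless the parents refuse contact, and add hospitalisation to its questions.
3. Define endpoint 8's time window and analyse it by randomised arm in all dosed children.
4. Exempt endpoint 8 from LOCF. Report children without a Day 14 outcome as unknown, with counts and reasons for leaving by arm.
5. Add a worst-case sensitivity count in which unknowns are treated as complications.

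The cost is a few extra phone calls, a short change to the protocol and analysis text, and a complication rate that may look less favourable.
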